**6.0 Procedures Involved\***

- 6.1 The study adheres to a randomized controlled trial (RCT) design. Participants will be randomized to either the TIP or HET condition. Randomization will be stratified based on undergraduate vs. community member status. For each group, a random number table will be generated in Excel with either 1 = TIP or 2 = HET assigned to each participant ID. After completion of consent, the participant will receive their ID (assigned in sequential order) and the research assistant will prepare the corresponding treatment.

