## PROTOCOL TITLE: Development and Evaluation of a Tonic Immobility Focused Psychoeducational Intervention - RCT

6.2 The study proposes to enroll 120 participants to test the efficacy of the TIP intervention, compared to a HET control condition. All data collection will be conducted using Qualtrics. The study will be comprised of a total of three time points: Baseline, Week 1 follow-up, and Month 1 follow-up.

First, eligible participants will read and sign an informed consent that outlines all study procedures, details limits to confidentiality, and emphasizes that participants may discontinue participation at any time with no penalty.

The first appointment, baseline, will include pre-intervention self-report measures, the completion of one of the two interventions (TIP or PHET), and post-intervention self-report measures. The baseline appointment is expected to take 90 minutes. Participants will be compensated with a \$30 gift card or 1.5 course credits. All baseline procedures will be conducted either in-person within the Anxiety and Behavioral Health Clinic research suite or virtually via HIPAA-compliant Zoom. For in-person sessions, all COVID-19 related federal, state, and local guidelines as well as FSU IRB regulations will be followed. See section 6.3 for further information on COVID-19 safeguards.

The second and third appointments, week 1 and month 1 follow-up, will be completed online. Participants will be contacted via email and asked to complete a battery of self-report measures via a Qualtrics survey link. The questionnaire is expected to last 30 minutes and participants will be compensated either a \$10 gift card or 0.5 course credits for the completion of each appointment.

After the completion of the month 1 follow-up appointment, participants will be debriefed and individuals in the control condition will be given the opportunity to receive the active treatment condition.

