## 10.0 Inclusion and Exclusion Criteria\*

10.1 Student participants who endorse prior TI experience during the subject pool screening process will be invited to complete a Qualtrics survey to determine eligibility. Interested participants will be asked to sign-up for the current study using the Sona-systems website. Community participants will be directed to the Qualtrics survey through flyers and online advertisements. Eligible community participants will be contacted via phone to schedule their initial appointment.

10.2 Eligible participants must be 18 years or older and have endorsed prior TI experience. Study participants will be selected for the

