## PROTOCOL TITLE: Development and Evaluation of a Tonic Immobility Focused Psychoeducational Intervention - RCT

current investigation based on prior TI experience (TIQ items A & B) and elevated posttraumatic stress symptoms (PCL-5). Exclusion criteria includes individuals who have not endorsed past TI behavior and are not 18 years or older.

*10.3 Indicate specifically whether you will include or exclude each of the following special populations: (You may not include members of the above populations as subjects in your research unless you indicate this in your inclusion criteria.)*

- *Adults unable to consent:* Excluded
- *Individuals who are not yet adult:* Excluded
- *Pregnant women:* Excluded
- *Prisoners:* Excluded

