*13.5 Describe as applicable whether and how subjects will be paid, earn course or other credits, reimbursed or provided with any financial or other incentive, token or gift for taking part in the research. Include a description and schedule of the total amount or value as well as the timing of any payments, credits, reimbursement or other incentive, token or gift. Indicate how if at all any amount is pro-rated for research visit or activity completion, and whether and how subjects' refusal to answer any question or subjects' withdrawal from or discontinuing taking part in the study or any study activity will reduce or preclude subjects from earning part or all of such any payment, credit, reimbursement or other incentive, token or gift.*

*Also describe the proposed method (how, by whom, form etc.) of payment/disbursement. While payment should not be contingent upon completion of the entire study, a proportion or progressive partial payment as an incentive for completion of the study is acceptable.*

Student participants will receive 1.5 course credits for completion of the baseline appointment and 0.5 credits for each follow-up appointment. Thus, participants will receive 2.5 credits in total for completing all study appointments. Participants who refuse to answer any question or withdraw from the study will still receive compensation for their appointment.

Community participants will receive a \$30 gift card for completion of the baseline appointment and a \$10 gift card for each follow-up appointment. Thus, participants will receive \$50 in total for completing all study appointments. Participants who refuse to answer any question or withdraw from the study will still receive compensation for their appointment.

PROTOCOL TITLE: Development and Evaluation of a Tonic Immobility Focused Psychoeducational Intervention - RCT

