## PROTOCOL TITLE: Development and Evaluation of a Tonic Immobility Focused Psychoeducational Intervention - RCT

mediation models. Maximum likelihood and percentile bootstrapped CIs (with 5,000 resamples) will be used (Hayes & Scharkow, 2013; Preacher & Hayes, 2004).

17.2 *Describe the steps that will be taken to secure the data (e.g., training, authorization of access, password protection, encryption, physical controls, certificates of confidentiality, and separation of identifiers and data) during storage, use, and transmission.*

All data will be coded by arbitrary participant numbers to ensure confidentiality and will be stored using password protected documents. Specifically, once the participant is consented, they will be assigned a unique study ID, which will be used instead of their name on subsequent surveys. The document linking participant names to study IDs will be recorded in a password-protected Microsoft Excel document, which will be stored on a password-protected server inside the Anxiety and Behavioral Health Clinic (ABHC) research suite. Only ABHC study staff (i.e., PI, graduate students, and project coordinators) who have been trained in data management procedures will be able to access the data via password.

17.3 *Describe any procedures that will be used for quality control of collected data.*

See 17.4

17.4 *Describe how data or specimens will be handled study-wide:*

Data entry personnel will download the data into a dedicated, password-protected computer database. Computer files will be maintained on the servers and backed up daily. Computers and databases will be password protected with independent passwords known only to the PI and data entry personnel. Other safeguards include: (a) ensuring that all project staff are well informed about regulations pertaining to confidentiality, (b) the use of ID numbers as opposed to names on all data forms, (c) utilizing computer-based assessments whenever possible.

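### Section 6.1 describes no step that hides the allocation list or holds back the arm until the pre-intervention measures are done; separately, 17.1 puts the stratification factor in no model

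*Combined protocol and SAP*

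**What the plan says.** **Allocation (6.1).** The protocol states the stratification in one line: "Randomization will be stratified based on undergraduate vs. community member status". The list is then made separately within the two strata, in this way: "a random number table will be generated in Excel with either 1 = TIP or 2 = HET assigned to each participant ID". Once consent is complete, "the participant will receive their ID (assigned in sequential order) and the research assistant will prepare the corresponding treatment". Block size, the person who makes the list and the person who holds it are not stated.

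**Order of events.** Section 17.2 says that "once the participant is consented, they will be assigned a unique study ID, which will be used instead of their name on subsequent surveys". Section 6.2 places consent first and then says: "The first appointment, baseline, will include pre-intervention self-report measures, the completion of one of the two interventions (TIP or PHET"), followed by the post-intervention measures. All measures are self-report in Qualtrics.

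**Screening and scheduling.** Section 10.2 selects people for the "current investigation based on prior TI experience (TIQ items A & B) and elevated posttraumatic stress symptoms (PCL-5"), with no cut-off given. Section 10.1 has students sign up through Sona, while "Eligible community participants will be contacted via phone to schedule their initial appointment".

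**Analysis (17.1).** The plan lists hierarchical regressions for early outcomes, three multi-group latent difference score models (guilt, shame, PTSD symptoms) and two mediation models. Each is described in terms of condition. Student or community status appears in none of them, nor in the baseline check, which covers age, gender and TIQ total.

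**The concern.** Issuing IDs in sequence after consent conceals the next arm only if the people enrolling cannot see the list. Someone who saw both a screening PCL-5 score and the list could time an appointment or a consent to suit the next arm. Section 6.1 also does not say when, after consent, the assistant looks up the arm. It could therefore be known before the guilt, shame and PCL-5 scores that start change 1 in all three latent difference score models are complete. Concealment cannot be restored once enrolment is under way, and later readers cannot verify it if the protocol is silent.

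The second gap is of a different kind. The trial randomises within two groups and then does not carry the grouping into any model. The groups are also rewarded differently. "Student participants will receive 1.5 course credits for completion of the baseline appointment and 0.5 credits for each follow-up appointment"; community members receive gift cards. Return at follow-up may therefore differ by group, although the documents give no return rates. Section 17.1 relies on full information maximum likelihood for missing data, and that assumption is easier to defend with the grouping in the model.

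**Working it through.** **1. Search for a concealing step.** No section describes a third-party holder, a sealed list, central release, or a limit on who sees the table. The access rules do not settle it. Sections 15.1, 17.2 and 17.4 restrict passwords for participant data, while 7.1 and 19.3 give all study staff access to stored data or protected documents. None mentions the allocation table. Section 25.1 refers to written job protocols that are not part of these documents.

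**2. Size of possible steering.** The documents supply N = 120. The rest is assumed: 60 per arm, independent draws, two-sided 5% tests, a share q of adjacent pairs ordered so that the less severe person gets TIP, and a correlation rho of 0.5 to 0.7 between the steering score and the outcome.

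- The chance that the two arms in a pair differ is 0.5. The mean gap between the two ordered values of a normal pair is 2/√π = 1.128 SD.
- Pre-intervention gap: g = q × 0.5 × 1.128 = 0.564q, which is 0.056 SD at q = 10% and 0.113 SD at q = 20%.
- Post-score bias: rho × g. Noncentrality: bias × √30 (t, 118 df).
- Change-score bias: (1 − rho) × g, acting against TIP, because the more severe controls regress further towards the mean.

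| q | rho | Post-score bias (SD) | False-positive rate | Change-score bias against TIP (SD) |
|---|---|---|---|---|
| 10% | 0.5 | 0.028 | 5.3% | 0.028 |
| 10% | 0.7 | 0.039 | 5.5% | 0.017 |
| 20% | 0.5 | 0.056 | 6.1% | 0.056 |
| 20% | 0.7 | 0.079 | 7.1% | 0.034 |

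With the next arm hidden, the bias is 0. With adjustment for the score used to steer, it is also about 0. For scale, 60 per arm detects 0.52 SD with 80% power. The protocol gives no power calculation to compare this with.

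**3. Value of the stratum as a covariate.** Let the two groups differ by d SD on the outcome, with a share p in one group. Then v = d²p(1 − p), and the share of variance removed is v/(1 + v).

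| d | p = 0.5 | p = 0.75 | p = 0.5, pre-score in model, rho = 0.5 | same, rho = 0.7 |
|---|---|---|---|---|
| 0.2 | 1.0% | 0.7% | 0.3% | 0.2% |
| 0.5 | 5.9% | 4.5% | 2.0% | 1.1% |
| 0.8 | 13.8% | 10.7% | 5.1% | 2.7% |

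The last two columns use v = [d(1 − rho)]² × 0.25/(1 − rho²), assuming the same d at both times. If the stratum is unrelated to the outcome, the cost is one degree of freedom: 117/116 = 1.0086, about 0.9% in variance.

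**4. Validity without the stratum.** Unblocked lists made separately per stratum balance no better than simple randomisation, so an unadjusted test keeps about 5% error. If the lists were blocked, the unadjusted test would be conservative. Its error would be 2[1 − Φ(1.96/√(1 − R²))], with R² the share removed at p = 0.5: 4.9%, 4.3% or 3.5% for d = 0.2, 0.5 or 0.8. Neither case inflates error.

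**The case against.** The strongest reply is that this is missing description and not a shown defect. Eligibility is set by a Qualtrics survey, outcomes are self-reported, allocation follows consent, and the job protocols may already restrict the list. All of that stands. Nothing says that participants learn their arm before the pre-intervention measures, or that the assistant's lookup comes first, and no clear route is described by which the assistant's knowledge would alter self-reported scores.

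Steering could use only the screening PCL-5, so any gap in guilt or shame would be more diluted than the table shows. Sona sign-up leaves less room among students, although 13.3 can be read as phoning all eligible people. Applying q to all 120 is therefore generous.

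A reader might carry the whole pre-intervention gap into the outcome comparison and conclude that the false-positive rate reaches 6.1% at q = 10% and 9.4% at q = 20%. That would need a correlation of 1.0 between the steering score and the outcome. It also overlooks that the bias reverses in change scores, the form of comparison planned in the latent difference score models.

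On the stratum, 17.1 names no covariate at all, so this factor is not singled out, and hierarchical regression may imply earlier predictor steps whose contents are unstated. Not named is not the same as excluded. This lowers the weight of the second point but does not remove it: a factor used to randomise should be named in the models.

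**Conclusion.** Both gaps hold, at modest size. Section 6.1 does not show that the list is hidden or that the arm is released only after the pre-intervention measures. Under the steering assumptions above, the harm to an unadjusted post-score comparison is 0.03–0.08 SD for 10–20% of pairs, with a false-positive rate of 5.3–7.1%. In a change-score comparison the bias is about 0.03–0.06 SD against TIP at 20%. These figures illustrate scale and are not evidence of harm.

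Two stronger conclusions are tempting. One is that allocation was in fact open and enrolment was steered; the documents are silent on list handling, and silence does not establish that. The other is that leaving out the stratum invalidates the tests; it costs precision only, about 0.2–5% of variance once the pre-intervention score is in the model. The change is still worth making because it is cheap and concealment cannot be added afterwards. Confidence is medium, because the job protocols are not available.

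**What to change.** **Section 6.1.** Load each stratum's list into the existing Qualtrics baseline survey, or keep it in a file closed to staff who schedule, consent or run sessions. State who generates and holds it. Release the arm only after the pre-intervention measures are submitted. If the job protocols already do this, one sentence saying so is enough.

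**Section 17.1.** Include undergraduate or community status as a covariate in the regression, latent difference score and mediation models. In the multi-group models, regress the initial score and each latent change on the mean-centred indicator, with slopes equal across arms. In the mediation models, enter it in both the mediator and the outcome equation.

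**Cost.** One or two sentences in each section and a short Qualtrics set-up. The assistant learns the arm slightly later. The documents do not show that an independent list holder is available; the Qualtrics route avoids needing one during recruitment. Extra parameters are 1 per regression, 4 each for guilt and shame, 3 for PTSD symptoms, and 2 per mediation model. If the stratum is weakly related to the outcome, the precision gain is close to nil.

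Blocking is not proposed. Session staff will still see past arms, and an equal mix of blocks of 4 and 6 would raise the rate of correct guesses from 50% under independent draws to (2.833 + 4.100)/10 = 69%.

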## PROTOCOL TITLE: Development and Evaluation of a Tonic Immobility Focused Psychoeducational Intervention - RCT

6.2 The study proposes to enroll 120 participants to test the efficacy of the TIP intervention, compared to a HET control condition. All data collection will be conducted using Qualtrics. The study will be comprised of a total of three time points: Baseline, Week 1 follow-up, and Month 1 follow-up.

First, eligible participants will read and sign an informed consent that outlines all study procedures, details limits to confidentiality, and emphasizes that participants may discontinue participation at any time with no penalty.

The first appointment, baseline, will include pre-intervention self-report measures, the completion of one of the two interventions (TIP or PHET), and post-intervention self-report measures. The baseline appointment is expected to take 90 minutes. Participants will be compensated with a \$30 gift card or 1.5 course credits. All baseline procedures will be conducted either in-person within the Anxiety and Behavioral Health Clinic research suite or virtually via HIPAA-compliant Zoom. For in-person sessions, all COVID-19 related federal, state, and local guidelines as well as FSU IRB regulations will be followed. See section 6.3 for further information on COVID-19 safeguards.

The second and third appointments, week 1 and month 1 follow-up, will be completed online. Participants will be contacted via email and asked to complete a battery of self-report measures via a Qualtrics survey link. The questionnaire is expected to last 30 minutes and participants will be compensated either a \$10 gift card or 0.5 course credits for the completion of each appointment.

After the completion of the month 1 follow-up appointment, participants will be debriefed and individuals in the control condition will be given the opportunity to receive the active treatment condition.

6.3 The risks to human subjects in the proposed study are minimal. Nevertheless, precautions will be taken to minimize participants' risk in the proposed study. All individuals will be informed of the nature of the investigation and the types of assessments and procedures. Participants will be asked to fill out an informed consent statement prior to participating in the project. Should a participant experience emotional distress including strong emotional or physical reactions to the intervention, a graduate-level therapist supervised by [name] will be called in to meet with the participant. Therapists will assist the participant in implementing coping skills to tolerate and reduce distress (e.g., deep breathing, self-soothing). [name] or an alternate clinical supervisor with the FSU Psychology Clinic will be on call for consultation as needed at all times.

PROTOCOL TITLE: Development and Evaluation of a Tonic Immobility Focused Psychoeducational Intervention - RCT

**6.4 Safeguards for Protecting Against COVID-19.** To reduce risk of COVID-19, our study team plans to follow standard COVID-19 precautions such as social distancing, mask wearing, and the sanitization of surfaces. However, participants will be informed that the voluntary disclosure of their full COVID-19 vaccination status is an alternative to COVID-19 related precautions, and they would be able to remove their masks during the baseline appointment. Staff will make a note in the study log of who has shown full COVID-19 vaccination documentation. The dialogue below will be said to participants when telling them about vaccination procedures:

- *"In order to protect against COVID-19 or Coronavirus, if you come to the lab we will follow certain precautions including social distancing and use of masks. However, we don't have to do this for persons who have completed a full COVID-19 vaccination. You may, if you'd like, share with us information about your COVID-19 vaccination, but this is your decision and is not required. You can still come to the lab and we will follow our usual COVID-19 precautions."*

**6.5** The following self-report measures will be used throughout the study.

**Demographic survey.** A self-report questionnaire will be used to assess participant demographic information. Specifically, various demographic variables will be assessed including gender, ethnicity, race, sexual orientation, and educational/occupational level.

**Adverse Childhood Experiences Questionnaire.** (ACE; Felitti et al., 1998) The ACE is a self-report measure designed to assess abuse, neglect, and caregiver dysfunction experienced during childhood (i.e. before the age of 18). Participants were asked to respond "yes" or "no" to 10-items representing different categories of adverse childhood experiences.

**Anxiety Sensitivity Index-3** (ASI-3; Taylor et al., 2007). The ASI-3 is an 18-item self-report questionnaire assessing levels of anxiety sensitivity. The ASI-3 is a widely used measure of fear of anxiety-related symptoms and sensations.

**Childhood Harshness & Unpredictability** (Maranges et al., Under Review). A brief self-report measure will be used to assess perceptions of harshness and unpredictability during childhood.

**Credibility/Expectancy Questionnaire** (CEQ; Devilly & Borkovec, 2000). The CEQ is a 6-item self-report measure of client's perceived expectations regarding the extent to which a treatment will reduce their symptoms.

## PROTOCOL TITLE: Development and Evaluation of a Tonic Immobility Focused Psychoeducational Intervention - RCT

**Life Events Checklist** (LEC-5; Weathers et al., 2013). The LEC-5 assesses the number and specific type of traumatic experiences an individual has experienced in their lifetime, as defined by Criterion A of the PTSD section of the DSM-5.

**Positive and Negative Affect Schedule** (PANAS; Watson et al., 1988). The PANAS is a 20-item self-report questionnaire assessing levels of positive and negative affect.

**Posttraumatic Stress Disorder Checklist for DSM-5** (PCL-5; Weathers et al., 2013). The PCL-5 is a 20-item self-report questionnaire used to assess PTSD symptoms.

**Posttraumatic Cognitions Inventory** (PTCI; Foa et al., 1999). The PTCI is a 33-item scale designed to assess negative cognitions about the self, negative cognitions about the world, and self-blame occurring post-trauma.

**Scale for Tonic Immobility Occurring Post-trauma** (STOP; Lloyd et al., 2019). The STOP is a 30-item self-report questionnaire designed to assess TI experiences occurring post-trauma.

**State Shame and Guilt Scale – 8** (SSGS-8; Cavalera et al., 2017). The SSGS-8 is a short version of the state shame and guilt scale designed to assess shame and guilt. This measure will be modified for the present study and participants will be asked to focus on their TI experience.

**Tonic Immobility Questionnaire** (TIQ; Taylor et al., 2007). The TIQ is a 12-item self-report questionnaire designed to assess TI experienced across a range of traumatic events.

**World Health Organization Disability Assessment Schedule 2.0** (WHODAS 2.0; Ustun, T.B. & World Health Organization, 2010). The WHODAS 2.0 is an assessment of difficulties due to health conditions in social, occupational, and daily life domains. A short version (21 items) of the WHODAS was compiled utilizing subscales that are relevant to mental health.

